10.3 Visit 2 (week 2)

Any Adverse Experiences will be recorded. Subject diary for adverse experiences and dosing compliance will be reviewed. Concomitant medications will be reviewed; abbreviated physical examination will be performed, vital signs will be recorded, CGI-SF, IIEF15, and ASEX will be completed. Eligible subjects will be scheduled for Visit 3 in 7 days.

10.4 Visit 3 (week 3)

Any Adverse Experiences will be recorded. Subject diary for adverse experiences and dosing compliance will be reviewed. Concomitant medications will be reviewed; abbreviated physical examination will be performed, vital signs will be recorded, Urinalysis for illicit drug and electrocardiography will be recorded. Approximately 5ml(1 teaspoon) of blood will be collected for liver function test: AST(GOT) and ALT(GPT). CGI-SF, IIEF15, and ASEX will be completed. Eligible subjects will be scheduled for Visit 4 in 7 days.

10.5 Visit 4 (week 4)

Any Adverse Experiences will be recorded. Subject diary for adverse experiences and dosing compliance will be reviewed. Concomitant medications will be reviewed; abbreviated physical examination will be performed, vital signs will be recorded, CGI-SF, IIEF15, and ASEX will be completed. Eligible subjects will be scheduled for Visit 6 in 7 days.

10.6 Visit 5 (week 5)

Any Adverse Experiences will be recorded. Subject diary for adverse experiences and dosing compliance will be reviewed. Concomitant medications will be reviewed; abbreviated physical examination will be performed, vital signs will be recorded, CGI-SF, IIEF15, and ASEX will be completed. Eligible subjects will be scheduled for Visit 6 in 7 days.

10.7 Visit 6 (week 6) (end of study drug)

Any Adverse Experiences will be recorded. Subject diary for adverse experiences and dosing compliance will be reviewed. Concomitant medications will be reviewed; abbreviated physical examination will be performed, vital signs will be recorded, Urinalysis for illicit drug and electrocardiography will be recorded. Approximately 5ml(1 teaspoon) of blood will be collected for liver function test: AST(GOT) and ALT(GPT). CGI-SF, IIEF15, and ASEX will be completed. CGI-SF, IIEF15, and ASEX will be completed.

10.8 Early Withdrawal Visit

Any Adverse Experiences will be recorded. Subject diary for adverse experiences and dosing compliance will be reviewed. Concomitant medications will be reviewed; abbreviated physical examination will be performed, vital signs will be recorded, Urinalysis for illicit drug and electrocardiography will be recorded.

11 STATISTICAL PLAN

11.1 Sample Size Determination

For the hypothesis testing of this study, the significance level was set at 5%. The hypothesis involves comparison of 2 groups on the mean of a continuous outcome. Each group of 35 provides 90% power to detect an effect size of 0.5.

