TEST PRODUCT, DOSE, AND ROUTE OF ADMINISTRATION	Bupropion hydrochloride sustained-release (Wellbutrin SR) 150mg once a day for 7 days then 150mg twice a day for 35 days. Taken orally by the subjects.
DURATION OF SUBJECT PARTICIPATION AND DURATION OF STUDY	Subjects will be on study for up to 63 days Screening: up to 7 days(1 week) Treatment: 42days (6 weeks) Follow-up: 14 days (2 weeks) The total duration of the study is expected to be 24 months. 20months for subject recruitment and 4 months for final subject follow-up.
EFFICACY EVALUATIONS	
PRIMARY ENDPOINT	
 Change from baseline International Index of Erectile Function (IIEF-15) score.
SECONDARY ENDPOINTS	
 Mean improvement in scores on the Clinical Global Impression Scale adapted for sexual Function (CGI-SF) Mean improvement in scores on the Arizona Sexual Experience

	
Scale (ASEX)
 
 • Safety and Tolerability
OTHER EVALUATIONS	
 • Montgomery-Åsberg Depression Rating Scale (MADRS- Malay version) • Mini International Neuropsychiatric Interview (M.I.N.I), • Opiate Treatment Index (OTI) • World health organization Quality of Life-Brief Scale (WHOQoL-Brief, Malay version) , • Malay Version of the Golombok-Rust Inventory of Marital State (Mal-GRIMS) • Rapid urine drug test
SAFETY EVALUATIONS	Incidence of adverse events
STATISTICS Primary Analysis Plan	Data will be analyzed using linear mixed-effects model.

TABLE OF CONTENTS	Pg
LIST OF ABBREVIATIONS	3
PROTOCOL SUMMARY	4
INTRODUCTION	9
1. BACKGROUND	9
1.1 Investigational Agent	10
1.2 Overview of Non-Clinical Studies	10
1.3 Overview of Clinical Studies	11
1.4 Risk / Benefit Assessment	11
1.4.1 Dose Rationale	11
1.4.2 Potential Risk	11
1.4.3 Potential Benefit	11
1.4.4 Risk Benefit Ratio	11
2 STUDY RATIONALE	12
3 STUDY OBJECTIVES	12
3.1 Primary Objective	12
3.2 Secondary Objectives	12
4 STUDY DESIGN	13
4.1 Design	13
4.2 Procedure	13
4.3 Project Timetable	14
5 CRITERIA FOR EVALUATION	14
5.1 Primary Efficacy Endpoint	14
5.2 Secondary Efficacy Endpoints	14
5.3 Safety Evaluations	14
6 SUBJECT SELECTION	15
6.1 Study Population	15
6.2 Inclusion Criteria	15
6.3 Exclusion Criteria	15
6.4 Subject Recruitment and Screening	15
7 EARLY WITHDRAWAL OF SUBJECTS	16
7.1 When and How to Withdraw Subjects	16
7.2 Data Collection and Follow-up for Withdrawn Subjects	17
8 STUDY TREATMENTS	17
8.1 Method of Assigning Subjects to Treatment Groups	17

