4.3 Project Timetable

The project will take 2 years. The plan is to randomize 1 subject per week, taking about 18 months to acquire 70 subjects. Follow-up evaluations will be completed 2 year from the start of the project.

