5 CRITERIA FOR EVALUATION

5.1 Primary Efficacy Endpoint

The primary endpoint to be measured in this study is:

- CGI-SF at the baseline, day 14(week 2), day 28(week four) and day 42 (week 6).

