Analyses of the Primary and Secondary Endpoints: The effect of Bupropion Hydrochloride Sustained-Release in improving the sexual dysfunction in the subjects is measured with CGI-SF at baseline, week 2, 4 and 6. The secondary outcomes are measured with IIEF15, its 5 domains and ASEX at baseline, week 2, 4 and 6. These repeated measurements will be analyzed using linear mixed-effects model. While these analyses are exploratory, they will provide useful information on differences in trends of reduction of depression and other outcomes between the Bupropion Hydrochloride Sustained-Release and placebo groups.

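### Section 11.1's 90% power does not follow from its own inputs: 35 per group, effect size 0.5 and 5% significance give about 54% two-sided, or 66% one-sided

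*Combined protocol and SAP*

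**What the plan says.** Section 11.1 sets significance at 5% and describes the test behind the sample size: "The hypothesis involves comparison of 2 groups on the mean of a continuous outcome". It then states: "Each group of 35 provides 90% power to detect an effect size of 0.5". It gives no sidedness, named test, SD, formula, correlation or dropout allowance, and it names no endpoint.

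The total of 70, 35 per arm, is repeated in the Protocol Summary and in sections 4.2 and 8.1, with 1:1 allocation in section 8.1. Section 13.2 says that withdrawals are not replaced.

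Section 11.2 plans a different analysis, of CGI-SF, IIEF-15 and ASEX at baseline and weeks 2, 4 and 6: "These repeated measurements will be analyzed using linear mixed-effects model". It does not name the contrast to be tested. It calls the analyses exploratory and says that they will inform on "differences in trends of reduction of depression and other outcomes between the Bupropion Hydrochloride Sustained-Release and placebo groups".

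The primary endpoint differs between places. The Protocol Summary has "Change from baseline International Index of Erectile Function (IIEF-15) score", while sections 3.1, 5.1 and 11.2 have CGI-SF.

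**The concern.** Section 11.1 contains everything needed to check its own figure: a significance level, a two-group comparison of means, a group size and an effect size. For a medium standardised effect of 0.5, 35 per group is far too few for 90% power by the usual calculation.

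This sentence is the only justification for enrolling 70 subjects. Anyone who relies on it, including an ethics committee, would take a non-significant result as fairly strong evidence against a 0.5 SD effect. If the real power is near one half, that reading is not warranted.

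**Working it through.** **Inputs.** From section 11.1: n = 35 per group, effect size d = 0.5 (read as a difference in means divided by the SD), alpha = 0.05, stated power 90%. Sidedness is not given, so both readings are shown.

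**Attempt to reproduce the 90%.** For a two-sample t-test, the noncentrality is d × sqrt(n/2) = 0.5 × sqrt(17.5) = 2.092, on 2 × 35 − 2 = 68 degrees of freedom.

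- Two-sided: critical value 1.995, power 54.1%.
- One-sided: critical value 1.668, power 66.5%.

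The normal approximation, Φ(2.092 − 1.960) and Φ(2.092 − 1.645), gives 55.2% and 67.2%. Every version falls at least 22 points short of 90%, so rounding or choice of software does not explain the gap.

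**Size needed for 90% at 0.5.** The normal formula is n = 2 × (z for alpha + z for power)² / d².

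- Two-sided: 2 × (1.960 + 1.282)² / 0.25 = 84.1, so 85. The t-test solves to 85.03, so 86.
- One-sided: 2 × (1.645 + 1.282)² / 0.25 = 68.5, so 69. The t-test solves to 69.20, so 70.

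**Effect detectable with 35 per group (t-test).**

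| Power | Two-sided | One-sided |
|---|---|---|
| 90% | 0.79 | 0.71 |
| 80% | 0.68 | 0.60 |

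**Where 90% might have come from.** The documents do not say. Two routes land close: a one-group, one-sided formula, (1.645 + 1.282)² / 0.25 = 34.3, and using the total of 70 as the size of each arm (one-sided power 90.3%). Both are conjecture, and neither is the design described. Reading 0.5 as Cohen's f, which is d = 1.0 for two groups, gives 98.5% two-sided and does not reproduce the figure either.

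**Could the mixed model supply it?** The plan gives no correlation, contrast or effect by visit, so the scenarios below are assumptions: SD 1, equal correlation rho between all visits, no missing data. In each, the noncentrality is (effect on the contrast / SD of the contrast) × sqrt(17.5).

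1. Baseline-adjusted mean of weeks 2, 4 and 6, with an effect of 0.5 at all three; variance (1 + 2 rho)/3 − rho²; 67 df.
2. Baseline-adjusted week-6 contrast, effect 0.5; variance 1 − rho²; 67 df.
3. Effect building linearly (0.167, 0.333, 0.5), baseline-adjusted, with optimally weighted visits; 67 df.
4. The same build-up tested as a difference in slope over weeks 0, 2, 4 and 6; slope difference 0.5/6; variance (1 − rho)/20; 68 df.

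| Scenario | Two-sided, rho 0.3 / 0.5 / 0.7 | One-sided, rho 0.3 / 0.5 / 0.7 |
|---|---|---|
| 1 | 87 / 89 / 96% | 93 / 94 / 98% |
| 2 | 58 / 66 / 82% | 70 / 77 / 90% |
| 3 | 66 / 72 / 86% | 77 / 82 / 92% |
| 4 | 45 / 58 / 80% | 58 / 70 / 88% |

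Scenario 2 reaches 90% at rho of about 0.77 two-sided or 0.71 one-sided. Missing data would lower all of these figures.

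**The case against.** The best defence is that the t-test is not the planned analysis. Section 11.1 names no test, section 11.2 plans a repeated-measures mixed model, and scenario 1 gives 87 to 96% two-sided, which brackets the stated 90%. The hypothesis in section 3.1 is directional, and a one-sided reading raises every figure. The trial is phase II, and section 11.2 calls its analyses exploratory.

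Part of this stands. 54% is the power of the comparison that section 11.1 describes, not a figure for the mixed model, whose power cannot be derived from the plan. It also stands that a mixed model could approach or exceed 90%.

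The rest does not rescue the statement. Section 11.1 does not invoke the mixed model or any correlation. Scenario 1 needs the full effect at week 2, held through week 6, with the visits averaged; section 3.1 frames the hypothesis as baseline to week 6, which is closer to scenario 2. Scenario 4 should carry little weight, because the sentence on trends that prompts it refers to depression, which is not an efficacy endpoint, and the linear build-up is assumed. One-sided testing still leaves the two-group comparison at 66%. Phase II or exploratory status may justify accepting lower power, but it does not make a stated 90% correct, and sections 3.1 and 11.1 are both written in terms of testing a hypothesis.

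**Conclusion.** The 90% is wrong as written. On section 11.1's own inputs the power is 54% two-sided or 66% one-sided, so the chance of missing a true 0.5 SD effect is about 46% or 34%, not 10%. This rests on reading the effect size as a standardised mean difference and on complete data; dropout would lower the power further.

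For the planned mixed model, the correct statement is that its power is unknown. It ranges from about 45% to 98% over the scenarios shown, depending on choices that the plan leaves open. The conclusion about the 90% holds whichever endpoint is primary. The figure must be corrected because it is the sole basis for the sample size.

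**What to change.** Reword section 11.1 in one of two ways.

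- **Keep the two-group comparison.** For example: *With 35 subjects per group, a two-sample t-test at two-sided 5% significance has about 54% power for a standardised difference of 0.5, and 90% power for a standardised difference of 0.79.*
- **Base the power on the mixed model.** State the sidedness, the contrast tested, the correlation between visits, the assumed effect at each visit and the allowance for missing data. Then recompute and report the result.

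In either case, name the endpoint to which the effect size applies, once the Protocol Summary (IIEF-15) has been reconciled with sections 3.1, 5.1 and 11.2 (CGI-SF).

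The cost is one rewritten paragraph and probably a less favourable power or detectable effect. Enrolment need not change; whether the lower power is acceptable is the sponsor's decision. If the sponsor instead wants 90% at 0.5 with a two-sided t-test, that is 2 × 86 = 172 subjects before dropout. Section 4.3 says: "The plan is to randomize 1 subject per week, taking about 18 months to acquire 70 subjects". At one per week, 172 subjects take 172 weeks, about 3.3 years; at 70 per 18 months they take 172 × 18/70 = 44 months. Either exceeds the 2-year project before follow-up is counted.

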11.2 Statistical Methods

Data Screening and Cleaning: Principal investigator will perform the data analyses. Prior to performing analyses, standard data screening/cleaning procedures will be applied. These procedures will screen the data for data-entry errors, check for outliers, assess the extent and pattern of missing data, and check that appropriate assumptions of Normality are met whenever necessary. Because of the size of the sample, it is unlikely that the randomization will result in significant imbalance of the distributions of demographic or other variables across the treatment groups. However, the randomization will be checked by comparing the groups on relevant background variables. The comparisons will use

analyses of variance for continuous variables and log-linear models for discrete or ordinal responses. Variables on which the groups show significant differences may be included as covariates in later analyses.

Linear Mixed Model: The analyses described below will involve the use of linear mixed model. These models extend the traditional repeated-measures framework in several ways. The main advantage is that it allows flexible regression modeling of patterns over time. It deals easily with measurements at irregular time points and automatically deals with missing data. It also allows a variety of structures for residual variations and correlations. In the present setting, the main explanatory variables will be medication group and time. Additional terms and random effects are included for each individual to model the correlation between observations on the same individual. In terms of missing data, they require that the data be missing at random, which is often reasonable. This means that the linear mixed model effectively assume that the missing data are similar to the observed data that do not drop out. In all analyses, the assumptions underlying the application of all the statistical methods that are used will be examined, principally through the use of standardized residuals, influence diagnostics, and graphical displays.

Analyses of the Primary and Secondary Endpoints: The effect of Bupropion Hydrochloride Sustained-Release in improving the sexual dysfunction in the subjects is measured with CGI-SF at baseline, week 2, 4 and 6. The secondary outcomes are measured with IIEF15, its 5 domains and ASEX at baseline, week 2, 4 and 6. These repeated measurements will be analyzed using linear mixed-effects model. While these analyses are exploratory, they will provide useful information on differences in trends of reduction of depression and other outcomes between the Bupropion Hydrochloride Sustained-Release and placebo groups.

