8 STUDY TREATMENTS

8.1 Method of Assigning Subjects to Treatment Groups

Up to 70 eligible patients will be randomly assigned to Bupropion Hydrochloride Sustained-Release or placebo treatment groups in a 1:1 ratio using a computer-generated table of random numbers through the use of the Randomization.com program. Subjects will be randomized to to Bupropion Hydrochloride Sustained-Release 150mg b.d. (n = 35) or placebo b.d (n = 35)

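### Section 11.2 fixes no covariance structure for the repeated scores; a random-intercept-only fit, which the text permits, would run the 5% baseline-to-week-6 test at about 9-12% if correlation fades over time

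*Combined protocol and SAP*

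**What the plan says.** Section 11.2 (Linear Mixed Model) first describes mixed models in general and notes that they can accommodate various residual correlation structures. It then turns to this trial. Medication group and time are the main explanatory variables, and "Additional terms and random effects are included for each individual to model the correlation between observations on the same individual". The random effects are not identified as an intercept, a slope or both. No residual structure is chosen. The time coding and the model term to be tested are not given either.

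Model assumptions are to be examined "principally through the use of standardized residuals, influence diagnostics, and graphical displays". No rule says what happens to the covariance if those checks look poor.

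For the endpoints, the same section has the primary outcome "measured with CGI-SF at baseline, week 2, 4 and 6", the IIEF-15, its domains and ASEX at the same times, and states that "These repeated measurements will be analyzed using linear mixed-effects model". The hypotheses in sections 3.1 and 3.2 all concern improvement from baseline to week 6. Section 11.1 states that "the significance level was set at 5" percent.

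**The concern.** Baseline and week 6 are 42 days apart; week 4 and week 6 are 14 days apart. A random intercept with independent residuals treats both pairs as equally correlated. If correlation in fact falls with the interval, the model uses an average correlation that is too high for the widest pair. It then understates the variance of the baseline-to-week-6 change, which is the contrast named in every hypothesis.

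The primary comparison would then have a confidence interval that is too narrow and a true significance level above the stated 5%. The same would apply to any secondary scale that shows the same correlation pattern; the documents give no evidence on this for any scale.

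**Working it through.** **Inputs from the documents.** 35 men per arm, "treatment groups in a 1:1 ratio" (sections 8.1 and 11.1); four equally spaced occasions (section 11.2); a 5% level (section 11.1); the contrast is the group difference in change from baseline to week 6 (section 3.1).

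**Assumptions, not in the documents.** Two-sided test, complete data, no true effect, equal SDs at all visits unless stated, and correlation ρ per two weeks decaying geometrically, so that baseline and week 6 correlate at ρ³.

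**Formulas.** Let s² be the variance at each visit. In a group-by-visit model with a random intercept, the model's variance for a man's week-6 minus baseline change is 2s²(1 − r̄), where r̄ is the mean of the six pairwise correlations, (3ρ + 2ρ² + ρ³)/6. The true variance is 2s²(1 − ρ³). Hence

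SE ratio R (true/model) = √[(1 − ρ³)/(1 − r̄)], and actual error = 2[1 − Φ(1.96/R)].

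**The plan's own level first.** With constant correlation, R = 1 and the error is 5.0%, so the stated 5% is reproduced when the random-intercept assumption is true.

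**Worked case, ρ = 0.7.** r̄ = (2.1 + 0.98 + 0.343)/6 = 0.5705. R = √(0.657/0.4295) = 1.237. The model SE is 1/1.237 = 0.81 of the true SE. Error = 2[1 − Φ(1.585)] = 11.3%.

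| ρ per two weeks | r̄ | ρ³ | R | Model SE too small by | Error, formula | Error, simulated |
|---|---|---|---|---|---|---|
| 0.5 | 0.354 | 0.125 | 1.16 | 14% | 9.2% | 9.2-9.3% |
| 0.6 | 0.456 | 0.216 | 1.20 | 17% | 10.3% | 10.1-10.2% |
| 0.7 | 0.570 | 0.343 | 1.24 | 19% | 11.3% | 11.3-11.5% |
| 0.8 | 0.699 | 0.512 | 1.27 | 21% | 12.4% | 12.3% |

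The simulated column gives the range over two independent sets, of 20,000 and 40,000 trials per setting. With an unstructured covariance, which for complete data is the t-test on the change, simulated error was 4.8-5.1%.

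**Other patterns, still fitting a random intercept only.**
- ρ = 0.3 gives 7.3%; ρ = 0.9 gives 13.4%.
- Decay plus a stable between-man component gives the same error as decay alone, because the component cancels from both variances.
- Constant correlation 0.6 with baseline SD 0.7 of the later SD: mean variance 0.8725, mean covariance 0.51, model variance 2 × 0.3625 = 0.725, true variance 0.49 + 1 − 0.84 = 0.65, so R = 0.947 and the error is about 3.8%.
- Decay (ρ 0.5-0.8) with baseline SD 0.7-0.85 of the later SD gives 7.0-11.2%.
- Data generated from true random slopes give 6.5-11.0% for the slope variances tried.

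**Other random effects.** A group-by-visit model with random intercept and slope, fitted to geometrically decaying data with ρ 0.5-0.8, gives about 4.3%. With linear time, simulation gave about 15% with an intercept alone and about 6% once a slope was added. Each rests on only 300 trials; at 6% the Monte Carlo standard error is √(0.06 × 0.94/300) = 1.4 points.

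**Other tested terms, random intercept only, ρ 0.5-0.8.** Linear group-by-time slope 11-15%; joint 3-df interaction 5.8-6.5%; overall group effect about 5%.

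**Price of the unstructured model if correlation is constant.** Degrees of freedom fall from 70 × 3 − 6 = 204 to 70 − 2 = 68. The interval widens by 1.9955/1.9717 = 1.012, or 1.2%.

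**The case against.** A reader might infer that the plan commits to a random intercept as its only device, so that the primary test really runs at 9-12%. The text does not support that. It refers to additional terms as well as random effects, and it mentions residual correlation structures a few sentences earlier. A random slope fits the wording equally well, and the section's interest in patterns and trends over time makes a slope a natural choice. With one, little or no inflation remains. The decay pattern is also assumed: equal SDs, geometric decay and complete data are all supplied from outside. Entry requires established sexual dysfunction, so a narrower baseline spread is plausible, and that lowers the figures. These objections stand, which is why the figure can only be conditional.

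Section 11.2 also names no tested term, and some terms in the same model are barely affected. That is true of the section read alone, but the hypotheses in sections 3.1 and 3.2 consistently name the baseline-to-week-6 comparison.

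The listed checks are introduced as the principal ones, so a check of the covariance is not ruled out. What is missing is any rule that follows from a check.

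Finally, section 11.2 calls the analyses exploratory. Section 11.1 nevertheless sets a 5% level for hypothesis testing, and the mixed model is the only analysis given for the primary endpoint, so its error rate still matters.

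**Conclusion.** The point holds in conditional form. Section 11.2 leaves the covariance open, and a random-intercept-only fit would comply with it. Under that fit, with geometric decay of 0.5-0.8 per two weeks, the standard error of the baseline-to-week-6 contrast is 14-21% too small and the nominal 5% test runs at about 9-12%. Across the other patterns examined for that fit, the error runs from about 4% to 13%, and it is 5% when correlation is constant.

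The documents do not show that the trial's test is inflated. They show that the plan permits a fit whose error rate depends on a correlation pattern it does not report. An unstructured covariance does not depend on knowing that pattern, so the case for it does not require the decay assumption to be right.

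The power statement in section 11.1 is a separate matter and does not bear on this conclusion.

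**What to change.** Replace the random-effects sentence in section 11.2 with wording such as:

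> CGI-SF at baseline and weeks 2, 4 and 6 will be analysed with a group-by-visit model with an unstructured covariance matrix across these four occasions, fitted by REML with Kenward-Roger degrees of freedom. The test is the group difference in change from baseline to week 6. If the model does not converge, heterogeneous Toeplitz and then heterogeneous AR(1) covariance will be used, in that order, with small-sample-corrected sandwich standard errors. IIEF-15, its domains and ASEX will be analysed in the same way.

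The SAP should also name the small-sample correction and its degrees of freedom.

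The four occasions must be listed. Sections 10.4 and 10.6 also record the three scales at weeks 3 and 5, whereas sections 5.1, 5.2 and 11.2 and Appendix 1 use baseline and weeks 2, 4 and 6 only. Four occasions need 4 × 5/2 = 10 covariance parameters; six would need 6 × 7/2 = 21.

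The change is to SAP wording only. Its cost is ten covariance parameters estimated from 70 men, and an interval about 1% wider if correlation is truly constant.

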1.1 Investigational Agent

Bupropion hydrochloride sustained-release (Trade name is Wellbutrin SR™), an antidepressant of the aminoketone class, is an inhibitor of the neuronal reuptake of norepinephrine and dopamine, and does not inhibit the reuptake of serotonin. Its structure closely resembles that of diethylpropion; it is related to phenylethylamines. It is designated as (±)-1-(3-chlorophenyl)-2-[(1,1-dimethylethyl)amino]-1-propanone hydrochloride. The molecular weight is 276.2. The molecular formula is C₁₃H₁₈ClNO•HCl.[20]

Bupropion is extensively metabolized in humans. Three metabolites are active: hydroxybupropion, which is formed via hydroxylation of the tert-butyl group of bupropion, and the amino-alcohol isomers, threohydrobupropion and erythrohydrobupropion, which are formed via reduction of the carbonyl group. The elimination half-life of metabolites are ranged from 20 hours to 37 hours. [20]

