3 STUDY OBJECTIVES

3.1 Primary Objective

- 3.1.1 To assess the clinical efficacy of bupropion hydrochloride sustained-release in the treatment of sexual dysfunction in men on methadone maintenance therapy.

Hypothesis

Bupropion hydrochloride sustained-release treated subjects will show significant improvement in Clinical Global Impression Scale adapted for Sexual Function (CGI-SF) then placebo treated subjects between baseline and week 6.

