APPENDIX 1:

	Screening test	During treatment with the study drug						
Time	baseline	1 week	2 week	3 week	4 week	5 week	6 week	At withdrawal
Visit	Visit 0	Visit1	Visit2	Visit3	Visit4	Visit5	Visit6	
Informed consent	√							
Prescription of study drug		√	√	√	√	√	√	
Treatment compliance		√	√	√	√	√	√	√
Interview for assessment of sexual dysfunction(1)	√		√		√		√	√
New symptoms that occur during treatment with the study drug		√	√	√	√	√	√	√(until 14 days)
Body weight		√	√	√	√	√	√	√
Blood pressure/pulse rate/body temperature		√	√	√	√	√	√	√
Blood test (2)	20ml			5ml			5ml	
Urinalysis(3)	√	√		√			√	
Electrocardiography	√	√		√			√	

- (1) At baseline: Montgomery-Åsberg Depression Rating Scale (MADRS, Malay version), Mini International Neuropsychiatric Interview (M.I.N.I), Opiate Treatment Index (OTI) and World health organization Quality of Life-Brief Scale (WHOQoL-Brief, Malay version, Malay Version of the Golombok-Rust Inventory of Marital State (Mal-GRIMS), International Index of Erectile Function (IIEF), Clinical Global Impression Scale adapted for Sexual Function (CGI-SF), Arizona Sexual Experience Scale (ASEX). Then, IIEF, CGI-SF, ASEX at week 2, 4, and 6.
- (2) Blood test: Approximately 20 ml (4 teaspoons) of blood will be collected at visit 0 (baseline) for Full blood count, Renal function test, Liver function test, Fasting blood sugar, total testosterone (TT), free testosterone (FT), estradiol (E2), luteinizing hormone (LH), and prolactin. Hepatitis B, C and HIV. Approximately 5ml(1 teaspoon) of blood will be collected during visit 3 and 6 for liver function test: AST(GOT) and ALT(GPT).
- (3) Urinalysis for illicit drug

20 REFERENCES:

1. Laumann, E.O., A. Paik, and R.C. Rosen, *Sexual dysfunction in the United States*. JAMA: the journal of the American Medical Association, 1999. **281**(6): p. 537-544.
2. Macdonald, S., et al., *Nithsdale Schizophrenia Surveys 24: sexual dysfunction Case—control study*. The British Journal of Psychiatry, 2003. **182**(1): p. 50-56.
3. Rosen, R.C., *Prevalence and risk factors of sexual dysfunction in men and women*. Curr Psychiatry Rep, 2000. **2**(3): p. 189-95.
4. Grube, M. and H. Weigand-Tomiuk, *Sexual dysfunctions in a group of psychiatric in-patients*. Psychiatrische Praxis, 2002. **29**(4): p. 194.
5. Oksuz, E. and S. Malhan, *The prevalence of male sexual dysfunction and potential risk factors in Turkish men: a Web-based survey*. International journal of impotence research, 2005. **17**(6): p. 539-545.

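### Section 11.2 calls the primary analysis exploratory, against the powered 5% hypothesis test in 3.1 and 11.1, leaves its contrast open, and names a depression trend that the schedule cannot supply

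*Combined protocol and SAP*

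**What the plan says.** The paragraph of section 11.2 on the primary and secondary endpoints gives CGI-SF as the measure of effect and IIEF-15, its five domains and ASEX as secondary outcomes. All are taken at baseline and weeks 2, 4 and 6 and analysed by linear mixed-effects model. It closes: "While these analyses are exploratory, they will provide useful information on differences in trends of reduction of depression and other outcomes", and the sentence goes on to say that the differences are those between the two arms.

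Three other places bear on that sentence.

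- Section 3.1 gives the primary hypothesis: bupropion "treated subjects will show significant improvement in Clinical Global Impression Scale adapted for Sexual Function (CGI-SF"), relative to placebo, between baseline and week 6.
- Section 11.1 reads "For the hypothesis testing of this study, the significance level was set at 5" per cent, then "The hypothesis involves comparison of 2 groups on the mean of a continuous outcome" and "Each group of 35 provides 90% power to detect an effect size of 0.5".
- Appendix 1, note 1, lists MADRS among the baseline scales and continues "Then, IIEF, CGI-SF, ASEX at week 2, 4, and 6". Sections 6.4 and 10.1 also place MADRS at screening. The protocol summary lists it under other evaluations, without a time.

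The protocol summary names change in IIEF-15 as the primary endpoint, whereas sections 3.1 and 5.1 name CGI-SF.

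**The concern.** The closing sentence is part of the operative analysis text. It is also the only sentence in section 11.2 that says what between-arm information the efficacy models will deliver. It gives those models a status that two other sections deny, describes a comparison different from the one in the primary hypothesis, and mentions by name only an outcome that the trial does not follow.

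At stake is what may be said of the result. If the text stays as it is, a significant CGI-SF difference could be reported as the planned test by citing 3.1 and 11.1, and a null one could be set aside as exploratory by citing 11.2. A choice of label or contrast made after unblinding would not be credible, the more so because section 11.2 has the principal investigator perform the analyses.

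**Working it through.** **1. The plan's own figure.** The only figures attached to the primary test are in section 11.1: 5% level, 35 per arm, standardised effect 0.5, power 90%. Sidedness, endpoint and standard deviation are not given. For two independent means, power ≈ Φ(d·√(n/2) − z).

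- d·√(n/2) = 0.5 × √17.5 = 2.092.
- Two-sided: Φ(2.092 − 1.960) = Φ(0.132) = 55.2% (54.1% by the t-test).
- One-sided: Φ(2.092 − 1.645) = Φ(0.447) = 67.2% (66.5% by the t-test).

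The 90% is not reproduced on either reading. From n = 2(z_α + z_β)²/d², 90% power needs 85 per arm two-sided or 69 one-sided. This is a separate problem, and the present point neither depends on it nor resolves it. What matters here is that section 11.1 claims a powered hypothesis test at all.

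**2. What the exploratory label covers.** The paragraph concerns the primary and secondary endpoints, and the sentences before the label describe only the mixed models of CGI-SF, IIEF-15, its five domains and ASEX. The phrase can refer to nothing else. It therefore covers 1 primary and 1 + 5 + 1 = 7 secondary outcomes alike. No other paragraph defines a separate confirmatory test.

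**3. Which contrast is tested.** Section 3.1 compares change between baseline and week 6. Section 11.2 promises differences in trends, and its general account of the mixed model says only that group and time are the main explanatory variables. It names no interaction, time point or test. With two arms and four time points, at least three tests fit that description:

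- the arm difference in change at week 6 (1 degree of freedom);
- the arm difference in linear slope (1 degree of freedom);
- the overall group-by-visit interaction, with (2 − 1) × (4 − 1) = 3 degrees of freedom.

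They answer different questions and can disagree on the same data. Only the first matches section 3.1.

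**4. Which outcomes can show a trend.** Scheduled assessments, from sections 5.1, 5.2, 6.4 and 10.1 and Appendix 1:

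| Scale | Baseline | Week 2 | Week 4 | Week 6 | After baseline |
|---|---|---|---|---|---|
| CGI-SF | yes | yes | yes | yes | 3 |
| IIEF-15 | yes | yes | yes | yes | 3 |
| ASEX | yes | yes | yes | yes | 3 |
| MADRS | yes | no | no | no | 0 |

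The visit text in sections 10.4 and 10.6 adds CGI-SF, IIEF-15 and ASEX at weeks 3 and 5, but never MADRS. The early withdrawal visit (10.8) lists no rating scale. Appendix 1 ticks the sexual-dysfunction interview at withdrawal without naming scales, and section 7.2 gives withdrawn subjects the end-of-study assessments, which do not include MADRS (10.7). With no value after baseline, neither a change nor a group-by-time trend in depression exists to be estimated. Depression is not an objective or endpoint in sections 3 or 5 either.

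**The case against.** The strongest reply is that this is loose drafting with little consequence. The trial is a single-centre phase II study and never calls itself confirmatory; such a trial may set a level and a power and still treat its results as exploratory. The between-arm targets are given outcome by outcome in sections 3.1 and 3.2. The word depression is probably carried over from another protocol, as the references to methylphenidate in sections 1.4.4, 12.2 and 17.1 appear to be.

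Much of this stands. The carry-over explanation is an inference, but it fits the documents better than an intended depression analysis with no data. Phase II status could justify an exploratory trial. It does not reconcile the sections, though: if the trial is exploratory, the hypothesis in 3.1 and the power statement in 11.1 need qualifying, and if it is not, the label in 11.2 is wrong. Stray wording in the operative analysis paragraph still has to be corrected.

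A reader might go further and infer that the stated analysis cannot be done, or that the only between-arm test is aimed at an unmeasured outcome. The documents do not support either. The same paragraph names CGI-SF as the measure of effect, the sentence itself adds other outcomes, and the three sexual-function scales are scheduled at all the times the models need. Only the depression trend is out of reach.

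A reader might also note that bupropion is "an antidepressant of the aminoketone class" and ask for MADRS to be repeated, to see whether any sexual-function gain accompanies a mood change. The trial does not pose that question, and not measuring it is no error in this plan.

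**Conclusion.** Wrong as written. Section 11.2 contradicts 3.1 and 11.1 on the status of the primary test, does not fix its contrast, and names a depression trend for which 0 post-baseline assessments are scheduled. The primary claim is weakened by the contradictory label and the open contrast; MADRS timing has no bearing on the CGI-SF test. No analysis of a declared endpoint is lost.

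The effect is on how the result may be interpreted, and no numerical size can be put on it. It would be excessive to infer that a significant CGI-SF result could never count as the planned test, because 3.1 and 11.1 do supply a hypothesis and a level. The fair conclusion is that the plan supports both readings and must choose one before unblinding.

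This rests on reading the label as applying to the models described just before it, and on the removed or attached material holding no separate analysis text or later MADRS schedule.

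**What to change.** First reconcile the primary endpoint between the protocol summary (IIEF-15) and sections 3.1 and 5.1 (CGI-SF); a sentence in 11.2 cannot settle the primary test while these differ. Then replace the closing sentence of that paragraph with:

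*The primary analysis tests the bupropion-placebo difference in change from baseline to week 6 in the single primary endpoint, estimated from the linear mixed model, at the 5% level (sidedness to be stated; two-sided proposed); all other analyses are secondary or exploratory.*

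This removes the mention of depression. The two-sided proposal is ours, since section 11.1 does not state sidedness. If the sponsor does intend an exploratory trial, keep the label and qualify the hypothesis in 3.1 and the power statement in 11.1 instead; the contrast should be named and depression deleted in that case too.

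The cost is wording only, to be settled before the database is locked and the blind broken. No visit, assessment or sample-size figure changes, and no MADRS repeat is needed.
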